Appendix 1: Abbreviations and Terms

Term	Definition
ACE2	Angiotensin converting enzyme 2
AE	Adverse event
COVID-19	Coronavirus disease
CQ	Chloroquine
DAIDS	Division of Acquired Immunodeficiency Syndrome
DAIDS	Division of acquired immunodeficiency syndrome
DBS	Dried blood spot
DSMB	Data and safety monitoring board
EC ₅₀	Half-maximal effective concentration
eCRFs	Electronic case report forms
Eligible	Qualified for enrollment into the study based upon adherence to inclusion/exclusion criteria
GFR	Glomerular filtration rate
HCQ	Hydroxychloroquine
HIPAA	Health Insurance Portability and Accountability Act
IATA	International Air Transport Association
ICF	Informed consent form
Index case	Term used throughout the protocol to denote the person with confirmed or suspected SARS-CoV-2 infection to whom the study participant was exposed
IRB	Institutional Review Board
MERS-CoV	Middle East respiratory syndrome coronavirus
Participant(s)	Term used throughout the protocol to denote the enrolled individual(s)
PCR	Polymerase chain reaction
PEP	Post-exposure prophylaxis
PK	Pharmacokinetic
RNA	Ribonucleic acid
SAE	Serious adverse event
SARS-CoV	Severe acute respiratory syndrome coronavirus
SARS-CoV-2	Severe acute respiratory syndrome coronavirus 2
SoA	Schedule of Activities
WHO	World Health Organization
WIRB	Western Institutional Review Board

Study conduct will be monitored by an independent monitor. Monitors will visit participating clinical research sites to review the individual participant records, including consent forms, electronic case report forms, supporting data, laboratory specimen records, and endpoints through laboratory and medical records (physicians' progress notes, nurses' notes, individuals' hospital charts), to ensure protection of study participants, compliance with the protocol, and accuracy and completeness of records. The monitors also will inspect sites' regulatory files to ensure that regulatory requirements are being followed and sites' pharmacies to review product storage and management.

Data and Safety Monitoring Board

An independent data and safety monitoring board (DSMB) will be convened for this study with expertise in coronavirus disease (COVID-19) or respiratory viruses, post-exposure prophylaxis (PEP), and emerging epidemics and a biostatistician. The purpose of the DSMB is to monitor the study for operational futility, social harms, and efficacy. The DSMB will evaluate the progress of the project, including periodic assessments of accrual, retention, safety, performance and variation of the project sites, and other factors that can affect project implementation.

The target number of households (index cases) and their contacts enrolled into the study will be re-assessed according to the distribution of cluster (household/institution) sizes seen in the study. The DSMB will review and approve modifications to the overall enrollment target. The DSMB will review the study after half to two-thirds of follow-up time with pre-specified stopping rules for efficacy and futility in terms of the efficacy of hydroxychloroquine (HCQ) PEP in reducing the incidence of SARS-CoV-2 infection overall and the ability of the study to meet its objectives. The DSMB will review severe acute respiratory syndrome coronavirus 2 (SARS-CoV-2) endpoints. The DSMB will consider factors external to the project when relevant information becomes available, such as policy changes or scientific developments that may have an impact on project implementation, safety, and integration of COVID-19 PEP into community-based disease prevention.

The DSMB will conduct interim reviews when adequate data have been accrued and convene by teleconference. Open reports containing accrual and retention rates, participant characteristics, and serious adverse events will be sent to the protocol team and DSMB members the week prior to the DSMB meeting. Only the DSMB members and the unblinded biostatistician will receive password-protected closed reports of SARS-CoV-2 endpoints by randomization arm.

Regulatory and Ethical Considerations

The study will be conducted according to Good Clinical Practice, the Belmont Report, and the Declaration of Helsinki. The study protocol, site-specific informed consent forms (ICFs), participant education and recruitment materials, and other requested documents—including any subsequent modifications—will be reviewed and approved by Western Institutional Review Board (WIRB), as the single IRB of record, responsible for oversight of research conducted at the study sites. Subsequent to initial review and approval, the WIRB will review the study at least annually.

Informed Consent Process

The principles of informed consent in the current edition of the Declaration of Helsinki will be implemented in each clinical study before any protocol-specified procedures or interventions are carried out. The consent form will describe the purpose of the study, the procedures to be followed, and the risks and benefits of participation. A copy of the consent form will be given to the participant, and this fact will be documented in the participant's record.

A participant who is rescreened is not required to sign another ICF; eligibility for the study must be re-checked prior to enrollment.

Study Records

Each study site will establish a standard operating procedure for confidentiality protection. Each site will ensure that study records including administrative documentation and regulatory documentation as well as documentation related to each participant enrolled in the study, including ICFs, locator forms, case report forms, notations of all contacts with the participant, and all other source documents are stored in a secure manner.

Confidentiality

Participants' study information will not be released without their written permission, except as necessary for oversight by:

- The protocol Co-Principal Investigators or designees
- Study funders
- WIRB
- New York University IRB
- University of Washington IRB

All laboratory specimens, evaluation forms, reports, and other records that leave the site will be identified by coded number only to maintain participant confidentiality. The exceptions are SARS-CoV-2 testing results which are subject to local and state reporting which is names-based. Local public health may contact participants diagnosed with SARS-CoV-2 for the purpose of surveillance and contact notification. Participants will be informed prior to SARS-CoV-2 testing that results are reportable and may lead to contact by local public health if results are positive for infection.

All records will be kept locked. All computer entry and networking programs will be done with coded numbers only. Clinical information will not be released without written permission of the participant, except as necessary for monitoring by the IRB, Office for Human Research

Protections, other local, United States, and international regulatory entities as part of their duties, or the industry supporters or designees.

Appendix 3: Site-specific Protocol Addendum Template

PURPOSE: The use of this site-specific protocol addendum is recommended with a multi-site study.

The purpose of this site-specific protocol addendum is to obtain information describing the local site-specific elements for conduct of the Core Protocol. The descriptions should focus on who, what, and where of the local study activities.

INSTRUCTIONS:

1. Add the Name of the study site to the Title of the Protocol in the header of the document.
2. Please complete each section below. If general description language already appears in the Core Protocol, which adequately describes the local activity at the study site, a notation can be inserted in the given section that reads, “As described in the Core Protocol.”
3. Please identify the completed addendum document using a version number and date.
4. Please note: the site-specific protocol addendum will require review and approval by the local Institutional Review Board (IRB)/Ethics Committee (EC) of record for the study site.

Study Site Information:

Name of Institution/Company:

Address:

Study Site Information for the Site Investigator:

Name of Site Investigator:

Title:

Institution/Affiliation:

Address:

Telephone Number:

Cell/Other Number:

Fax Number:

Study Site Number:

Assurance Information:

United States Department of Health and Human Services Office for Human Research Protections
Assurance Federal Wide Assurance number:

Expiration Date:

IRB/Ethics Committee Information:

Name of Human Subjects Protection oversight office for study site:

Name and number of reviewing IRB/EC:

Telephone Number at Office:

Fax Number at Office:

If Available, Point of Contact at IRB/EC:

Name:

Telephone Number:

Local Site-Specific Information:

1. Identify key study personnel (include name, title, address, point of contact information).
2. Description of key study personnel roles and responsibilities.
3. Describe the local recruiting procedures and strategies. Provide copy of any site-specific recruitment material. Identification of personnel responsible for completing tasks.
4. Describe the local consenting process. Provide a copy of the site-specific consent form(s). If an Ombudsman is named for the study site, provide name, title, and point of contact information.
5. Identify local study collaborations at the site such as pharmacy, laboratories, and other institutional departments.
6. Describe the local specimen/sampling procedures in place. Include acquisition, disposition, storage, and unique coding. If samples will be kept for future use, describe procedures and the security measures for short-term and long-term management. Provide name of repository.
7. Describe the plan for on-site management of study records and data, and participant study records. Explain procedures and security measures in place for short-term and long-term management. Declare who will have access to data.
8. Describe the local measures in place to promote privacy and confidentiality.
9. Describe the local procedures in place for provision of care for the participant regarding research-related injuries.
10. Identify who the participant can contact locally should the participant have any questions regarding the research. Identify who the participant can contact should the participant have questions regarding their rights as a study participant. Include the points of contact information (name, title, and telephone number).
11. Describe the procedures in place to address Health Insurance Portability and Accountability Act requirements. If a separate authorization form will be used at the

study site, provide a copy or ensure appropriate language has been included in the consent document(s).

12. Describe any unique site-specific study procedures or supplemental activities.
13. Declare any unique study population/cultural influences, socioeconomic conditions, etc.
14. Declare any other site-specific reporting obligations and procedures. Name any additional oversight boards or committees.
15. Define abbreviations that may apply to the specific study site.

Appendix 4: Hydroxychloroquine Label

Generic hydroxychloroquine label (current as of June 2018) is available online at <https://dailymed.nlm.nih.gov/dailymed/drugInfo.cfm?setid=b82bbda6-64f2-4426-b4ec-254eeea895ae> and provided below.

Appendix 5: Physiologically Based Pharmacokinetic Modeling of Hydroxychloroquine Used for Post-exposure Prophylaxis

Appendix 6: Pharmacokinetic Sample Collection and Analysis

Collection of Blood

Skin puncture

1. Before skin puncture, the participant should warm his/her hands. The finger is massaged anterogradely to enrich the blood flow toward the puncture site.
2. Clean the skin of the palmar side of the tip of the distal phalanx of the third or fourth finger of the non-writing hand with a suitable disinfectant, for example, 70% isopropyl alcohol. Puncture the skin by a single-use safety lancet. The finger should be held in such a position that the gravity facilitates the collection of blood from the fingertip.
3. When collection of capillary blood by skin puncture is complete, place a bandage on the fingertip.

Preparation of Blood Spots

Preparation from blood collected by skin puncture

1. Wipe off the first drop of blood with a gauze pad because it may contain excess tissue fluids. Massage the finger again to increase blood flow at the puncture site. Transfer the following drop to one of the circles of a filter card without touching the surface directly with the fingertip. Allow the blood to be soaked into the texture of the filter by capillary forces only.
2. Let the next large drop of capillary blood form on the fingertip and collect it in the next circle. Continue this procedure until all necessary circles are filled or blood flow stops.
3. Do not squeeze or “milk” the finger excessively if the blood flow is not sufficient to fill all the required circles of the filter card. If blood flow stops, place a bandage on the fingertip. Perform a second skin puncture on another finger if more blood is needed for the examination.
4. For blood obtained by venipuncture, use syringe to apply approximately 100 μ L of blood on the filter paper.

Drying of Blood Spots

To dry the blood spots, put the filter cards on a clean paper towel and let them dry, preferably overnight (but for at least 4 hours), at room temperature in the absence of any external source of heat. When the drying process is complete, the blood spots have a uniformly dark brownish color and no red areas are visible anymore.

Storage and Transportation of Dried Blood Spots (DBS)

NOTE: Processing of the blood spots can be interrupted after drying. The filter cards can now be stored.

1. For storage, put the filter paper card in a single, gas-impermeable zipper bag, containing 1 to 2 desiccant sachets to protect the specimens from moisture. Optionally, add a humidity indicator card.
2. Store at ambient temperature until the DBS card is collected.

On the filter paper, the participant should record the following:

1. Date and time of sample
2. Date and time of last dose

Samples that appear to be collected according to the schedule of activities, which have the required amount of blood for a 5- to 6-mm punch and have the minimal required information (1 through 2 above), will be processed for hydroxychloroquine (and metabolite) concentration.

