
 To test the efficacy of HCQ (400 mg orally daily for 3 days then 200 mg orally daily for an additional 11 days, to complete 14 days) to prevent incident SARS-CoV-2 infection 2 weeks after completing therapy, compared to ascorbic acid among contacts of persons with SARS-CoV-2 infection 	
 PCR-confirmed SARS-CoV-2 infection (self-collected samples collected daily Day 1 through Day 14 and collected 2 weeks after cessation of treatment [i.e., Day 28])

 To test the efficacy of HCQ to shorten the duration of SARS-CoV-2 shedding among those with SARS-CoV-2 infection in the HCQ PEP group 	
 SARS-CoV-2 viral shedding by PCR

 To test the efficacy of HCQ to prevent incident COVID-19 	
 PCR-confirmed COVID-19 diagnosis post start of HCQ therapy
Exploratory	

 To conduct SARS-CoV-2 viral genotyping to assess the impact of HCQ on viral resistance to HCQ PEP 	
 Viral genotyping of SARS-CoV-2 in a subset of treated study participants who develop infection

 To assess adherence to HCQ PEP 	
 Self-reported daily dosing and study therapy concentration (if in sub-study) in study participants

 • To evaluate the pharmacokinetics (PK) of HCQ by infection status 	
 • HCQ blood concentration

 • To assess if there is an association between PK of HCQ and the efficacy and safety endpoints evaluated 	
 • HCQ blood concentration, tolerability, and efficacy

 • To evaluate if SARS-CoV-2 viral load in the index case is associated with SARS-CoV-2 infection in the contact 	
 • SARS-CoV-2 semiquantitative PCR and genotyping

 • To test the efficacy of HCQ to shorten the magnitude of SARS-CoV-2 shedding among those with SARS-CoV-2 infection in the HCQ PEP group 	
 • Daily SARS-CoV-2 semiquantitative PCR

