9.1. Close Contact Participants

9.1.1. Screening/Baseline Evaluation: Day 0/1

Participants will be assessed for study eligibility through a screening conducted through a web-based screening tool, HIPAA-compliant video conference (Telehealth), telephone, or text messaging.

Day 0 evaluations are as follows:

- Informed consent
- Collection of demographic information
- Collection of past and current medical conditions, including known pregnancy and/or lactation status
- Collection of concomitant medication information
- Collection of information regarding exposure to the index case
- Check of inclusion and exclusion criteria

Eligible participants will be randomized with all members of a household assigned to the same arm. Participants will receive a swab kit either via courier or mail, which includes a Quick Start Instruction Card, swabs, plastic tubes for swab collection, and a return box with affixed Category B UN3373 label, as required by International Air Transport Association (IATA) guidelines [36].

The participant will do the following on Day 1:

- Collect mid-nasal swab for PCR
- Take study therapy (HCQ or ascorbic acid, as assigned)
- Complete Daily Survey (online, Telehealth, telephone, or text messaging). This Survey will include confirmation of adherence to study therapy dosing and daily swab collection, concomitant medication review, and symptoms review.
- *If in DBS Sub-study, collect DBS samples for analysis of anti-SARS-CoV-2 antibodies (if possible).*

Instructions for skin puncture and DBS sample preparation are provided in [Appendix 6](#). A study team member will be available via Telehealth, telephone, or text messaging to provide support for completion of this study procedure.

Screening/Day 0 and Day 1 procedures may occur on the same day.

The index case SARS-CoV-2 positive test results will be confirmed through self-report of the contact participant. *If in the index case sub-study, shedding of SARS-CoV-2 will be assessed by PCR of a mid-nasal swab ([Section 9.2](#)).*

9.1.2. Day 2 Through Day 13

The participant will do the following every day from Day 1 through Day 13, inclusive:

- Collect mid-nasal swab for PCR
- Take study therapy (HCQ or ascorbic acid, as assigned)
- Complete Daily Survey (online, telephone, or text messaging). This Survey will include confirmation of adherence to study therapy dosing and daily swab collection, concomitant medication review, and symptoms review.

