- *If in DBS Sub-study, collect DBS samples for analysis of HCQ concentration at any time during this period (1 to 5 times) after study drug dosing has commenced. No more than 1 sample per day should be collected.*

A study team member will be available via Telehealth, text messaging, or telephone to provide support for completion of study procedures. The courier will collect the swabs at minimum within 1 or 2 days of Day 7 and Day 13 and potentially as frequently as daily.

9.1.3. Day 14

The participant will do the following on Day 14:

- Collect mid-nasal swab for PCR
- Take study therapy (HCQ or ascorbic acid, as assigned)
- Complete Daily Survey (online, telephone, or text messaging). This Survey will include confirmation of adherence to study therapy dosing and daily swab collection, concomitant medication review, and symptoms review.
- *If in DBS Sub-study, collect DBS samples for analysis of HCQ concentration, if not already collected.*

A study team member will be available via Telehealth, text messaging, or telephone to provide support for completion of study procedures.

Participants are instructed to place their self-collected nasal swabs directly into the plastic tube that is pre-labeled with a unique barcode. Next, participants are instructed to place the plastic tube containing the self-collected nasal swab into a specimen bag, pre-packaged with an absorbent sheet, and then place the specimen bag into the provided return shipping box. Category B UN3373 stickers are affixed to the outside of the return box. Previous testing has demonstrated that respiratory viral ribonucleic acid (RNA) is stable in room temperature for up to 1 week. The courier will collect the swabs at minimum within 1 or 2 days of Day 14.

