10.4. Dried Blood Spot Optional Sub-study

Up to 1800 participants will be enrolled in the DBS Sub-study. DBS will be requested, but not required, of all participants. For those study sites not wishing to participate in the DBS Sub-study, this will not be considered a protocol deviation.

Participants will receive instructions for DBS self-collection in writing, with telephone, Telehealth, and text messaging options as support. Once cards have been dried, they will be collected by the study courier and returned to the laboratory.

The aim of the DBS Sub-study is to evaluate HCQ drug concentrations as an adherence measure and the PK of HCQ. If serological assays for SARS-CoV-2 are available, DBS may be tested for SARS-CoV-2 antibodies.

Pharmacokinetics

The exposure-response relationship of HCQ in the PEP of participants exposed to SARS-CoV-2 has not been established. Population PK analyses can be used to further inform dose selection in other populations and support concentration-response investigations with efficacy and safety outcomes.

To accomplish this, sparse PK sampling techniques can be employed. This would involve collection of whole blood at 1 to 5 times after dosing has commenced. The time of collection post-dose can be random; however, no more than 1 sample per day should be collected.

Given the long half-life of HCQ, samples for several weeks after the last dose are also informative to the population PK model development.

The basic requirements for PK sampling are as follows:

- 1. Accurate record of time of the dose prior to the blood sampling (dd:mm:yy; hh:mm)*
- 2. Accurate recording of time of blood sampling (dd:mm:yy; hh:mm) for each blood sampling.*
- 3. Whole blood can be obtained by venipuncture or capillary blood by skin puncture using a lancet.*
- 4. Approximately 100 μ L of blood is then applied to filter paper as outlined in [Appendix 6](#).*

Anti-SARS-CoV-2 Antibody Testing

DBS sample for serology will be collected at Day 1 and Day 28 and tested for SARS-CoV-2 antibodies provided that an appropriate test is available.

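### Appendix 6 ties the HCQ assay to a participant-written last-dose time, which suits PK modelling but may select against people who took little or no drug when the concentration is read as adherence

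*Protocol*

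**What the plan says.** Protocol Appendix 6 asks the participant to write two items on the filter paper: when the sample was taken, and "Date and time of last dose". It then sets the conditions for the assay. "Samples that appear to be collected according to the schedule of activities", that hold enough blood for the punch and that "have the minimal required information (1 through 2 above), will be processed for hydroxychloroquine (and metabolite) concentration". The card has no way to state that no dose was taken, and there is no rule for an incomplete card or for filling a blank from another source.

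The result has two uses. Section 10.4 states: "The aim of the DBS Sub-study is to evaluate HCQ drug concentrations as an adherence measure and the PK of HCQ". Section 7.8 also lists the concentration under treatment compliance, and Section 4 names it, for sub-study members, as part of the endpoint for the exploratory objective "To assess adherence to HCQ PEP". Among the basic requirements for PK sampling, Section 10.4 lists "Accurate record of time of the dose prior to the blood sampling".

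Section 9.1.2 places concentration spots "after study drug dosing has commenced". A separate Daily Survey covers dosing: "This Survey will include confirmation of adherence to study therapy dosing and daily swab collection". SAP Section 5.2 summarises adherence from self-reported pill taking only.

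**The concern.** Self-reported dosing is the only adherence summary in the SAP, so the blood concentration is the one planned check that does not rest on the participant's word. Appendix 6 makes that check depend on the participant first writing down a dose. A person who took nothing has no last dose to write. A person who dosed irregularly may be less likely to fill in the field.

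If the cards that pass come disproportionately from people who took their tablets, blood-level adherence in the HCQ arm would look better than it was. This would matter most after a null primary result, when readers would look to drug levels to tell an ineffective drug from an untaken one.

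**Working it through.** **Plan's own figure.** The documents give no figure for card completeness, unassayed cards or blood-level adherence, so there is nothing to reproduce.

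**Direction and size, one card per person.** Let A be true adherence, ra the share of adherers' cards that carry a last-dose time, and rn the same share for non-adherers. Then

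apparent adherence = A·ra / (A·ra + (1 − A)·rn).

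A, ra and rn are assumptions. With ra = 95%:

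| True A | rn = 95% | rn = 80% | rn = 50% | rn = 20% |
|---|---|---|---|---|
| 60% | 60.0% | 64.0% | 74.0% | 87.7% |
| 80% | 80.0% | 82.6% | 88.4% | 95.0% |
| 90% | 90.0% | 91.4% | 94.5% | 97.7% |

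For A = 80%: 0.76/(0.76 + 0.16) = 82.6% at rn = 80%, and 0.76/(0.76 + 0.10) = 88.4% at rn = 50%. At equal completion there is no bias. If adherers leave the field blank more often (ra = 80%, rn = 95%), the sign reverses: 0.64/(0.64 + 0.19) = 77.1% for a true 80%.

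**Several cards per person.** Section 10.4 allows 1 to 5 samples. Suppose each person gives three cards, completes them independently, and counts if at least one passes (assumptions). With ra = 95% and rn = 50% per card, the person-level pass rates are 1 − 0.05³ = 99.99% and 1 − 0.50³ = 87.5%. Apparent adherence for a true 80% is then 0.7999/(0.7999 + 0.1750) = 82.0%, against 88.4% with one card.

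**Whom the field can exclude.**

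- *Took some doses and stopped.* These people have a last dose to write, so their cards can pass.
- *Never started.* The Schedule of Activities and Sections 9.1.2 and 10.4 place concentration spots after dosing has begun. These people are missing mainly because no concentration card is scheduled for them.
- *Day 1 and Day 28 cards.* The Schedule of Activities row names both HCQ concentration and antibodies and marks both days. Sections 9.1.1 and 9.1.4 describe those spots as for antibodies only. If the Schedule of Activities governs, a never-starter's Day 28 card is on schedule and the last-dose field is what stops the assay. If the visit sections govern, it would not be assayed for HCQ in any case.

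**What detection can show.** Section 3.2.4 gives a terminal half-life of about 40 days. The fraction remaining d days after the last dose is 0.5^(d/40): 88.6% at 7 days and 79.8% at 13 days. This applies to the terminal phase only, and most spots are taken during loading and daily dosing. It does suggest that someone who stopped early would still have detectable drug.

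**The case against.** The strongest reply is that the field excludes few people. Never-starters are already outside the sampling window, and people who stopped can still write a last dose. That the latter complete it less often is conjecture. A reader might infer that non-takers' cards are thrown away and that measured adherence is overstated. The documents support neither statement: Appendix 6 says which cards will be processed but not what happens to the rest, and the completion rates are unknown.

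A reader might also infer that a null trial would be misread. That would need a blood-level adherence analysis, and the SAP specifies none. It is limited to primary and secondary objectives, while adherence is exploratory and the sub-study is optional. Non-use is also visible elsewhere. Section 7.8 has staff check that the first day's medication was taken. The CONSORT diagram in SAP Section 5.1 counts those who did not receive their assigned intervention, with reasons, and those with data for each assay.

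Finally, a concentration measured during loading and daily dosing is easier to interpret with a dose time, which is a reason to keep asking for it.

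Most of this stands, and it limits the point. It does not remove it: a rule written for PK still controls a measurement with a second purpose, a person who took nothing cannot satisfy it, and nothing in the plan separates the two uses.

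**Conclusion.** The point holds as a selection risk, not as a demonstrated bias. Appendix 6 makes a self-reported dose a condition of the only adherence measure that is not itself self-report. Overstatement is the more plausible direction because it needs only that non-adherers complete the field less often than adherers. On the assumed rates, with 95% completion in adherers and one card each, the excess is 1.4 to 4.0 points when non-adherers complete 80% of cards and 4.5 to 14.0 points when they complete 50%, across true adherence of 60% to 90%. It is smaller with several cards each, zero at equal completion, and negative if adherers leave more blanks.

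The absence of never-starters comes mainly from the sampling window and should not be attributed to this field. The Schedule of Activities and the visit sections also disagree on the purpose of the Day 1 and Day 28 spots. Priority is modest: the affected endpoint is exploratory, it comes from an optional sub-study, and the primary analysis is untouched.

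**What to change.** - In Appendix 6, assay every scheduled card that has enough blood and a sample date.
- Require the last-dose time only for entry into the population PK model. Where it is blank, allow it to be filled from the Daily Survey if available. The protocol does not say whether the survey records clock time, so some entries may be usable only as dates.
- Add a no-dose-taken option to the card, so that a blank and a true absence of dosing can be told apart.
- Report by arm the number of sub-study members with no card and the number with an unassayed card, so that never-starters and selection remain visible.
- State that adherence will be judged from the concentration relative to the sampling day. Mere detectability would count early stoppers as adherent.
- Reconcile the Schedule of Activities with Sections 9.1.1 and 9.1.4 on whether the Day 1 and Day 28 spots are for HCQ concentration.

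The cost is wording in Appendix 6 and the visit sections, one extra box on the card, a short descriptive table, and a few more assays on cards already collected.
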